8.4.3 AD Sub-Study Network Neuroscience

Subjects who can undergo MRI will have scans obtained prior to treatment and at 6 months after the completion of TMS. All other details are as stated above, however, subject-specific lesion masks will not be relevant.

8.1.4 Safety Analysis

All data on any and all adverse events occurring during the baseline testing, 2 week period in which TMS is being administered, and the 6-month interval between the end of TMS and completion of the study will be used for an overall study safety analysis.

8.5 Subject Population(s) for Analysis

The subject population that will be subject to analysis will be the randomized population. Subjects that are non-compliant with treatment will be encouraged to continue with follow-up and these measurements will be enter into analysis (see 8.4.1 for details on the analysis of non-compliant subjects)

9 Safety and Adverse Events

9.1 Definitions

9.1.1 Adverse Event

An **adverse event** (AE) is any symptom, sign, illness or experience that develops or worsens in severity during the course of the study. Inter-current illnesses or injuries should be regarded as adverse events. Abnormal results of diagnostic procedures are considered to be adverse events if the abnormality:

- results in study withdrawal
- is associated with a serious adverse event
- is associated with clinical signs or symptoms
- leads to additional treatment or to further diagnostic tests
- is considered by the investigator to be of clinical significance

9.1.2 Serious Adverse Event

Adverse events are classified as serious or non-serious. A **serious adverse event** is any AE that is:

- fatal
- life-threatening
- requires or prolongs hospital stay
- results in persistent or significant disability or incapacity
- an important medical event

9.2 Recording of Adverse Events

At each contact with the patient, the investigator will seek information on adverse events by specific questioning and, as appropriate, by examination. Information on all adverse events will be recorded immediately in the source document, and also in the appropriate adverse event module of the case report form (CRF). All clearly related signs, symptoms, and abnormal diagnostic procedures results will be recorded in the source document.

All adverse events occurring during the study period will be recorded. The clinical course of each event will be followed until resolution, stabilization, or until it has been determined that the study treatment or participation is not the cause. Serious adverse events that are still ongoing at the end of the study period will be followed up to determine the final outcome. Any serious adverse event that occurs after the study period and is considered to be possibly related to the study treatment or study participation will be recorded and reported immediately to the chair of the DSMB.

9.3 Relationship of AE to Study

The relationship of each adverse event to the study procedures will be determined by the PI, who is a neurologist. Based on his expertise with TMS, he will make a determination about the relationship of the adverse event to the study procedures.

9.4 Reporting of Adverse Events, Adverse Device Effects and Unanticipated Problems

9.4.1 Follow-up report

If an SAE has not resolved at the time of the initial report and new information arises that changes the investigator's assessment of the event, a follow-up report including all relevant new or reassessed information (e.g., concomitant medication, medical history) should be submitted to the IRB. The investigator is responsible for ensuring that all SAEs are followed until either resolved or stable.

9.4.2 Investigator reporting: notifying the study sponsor

A serious adverse event will be reported to the IRB and chair of the DSMB by telephone within 24 hours of the event. A Serious Adverse Event (SAE) form will be completed by the investigator and faxed to the IRB within 24 hours. The investigator will keep a copy of this SAE form on file at the study site.

At the time of the initial report, the following information should be provided:

- Study identifier
- Study Center
- Subject number
- A description of the event
- Date of onset
- Current status
- Whether study treatment was discontinued
- The reason why the event is classified as serious
- Investigator assessment of the association between the event and study treatment

Within the following 48 hours, the investigator will provide further information on the serious adverse event in the form of a written narrative. This will include a copy of the completed Serious Adverse Event form, and any other diagnostic information that will assist the understanding of the event. Significant new information on ongoing serious adverse events will be provided promptly to the IRB and chair of the DSMB.

9.4.3 Investigator Reporting: Notifying the Penn IRB

Reports of all serious adverse events (including follow-up information) will be submitted to the IRB within 10 working days. Copies of each report and documentation of DSMB/IRB notification and receipt will be kept in the Clinical Investigator's binder.

9.5 Unblinding Procedures

Patients will be told which treatment (real TMS+CILT vs. sham TMS+CILT) they received at the completion of the entire study. If a serious adverse event should occur, the patient will be unblinded/unblinded.

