5.3 Blinding

Participants will not be informed of their assignment to active or sham status. Sham TMS will be administered with a sham TMS coil that looks and sounds like the active coil but does not generate a magnetic field. Surface electrodes applied to the scalp during sham stimulation will simulate the sensation of TMS, therefore allowing subjects with prior experience with TMS to be blind to condition as well.

The unblinded study coordinator will keep the master file of subject assignments. This individual will administer TMS, but all other individuals in contact with the subject or their data will be unaware of group assignment. In particular, the speech-language pathologist (SLP) and the individuals administering and scoring the language measures will not be present for the administration of TMS and will be blinded with respect to subject assignment. In the case of an adverse event, the blind may be broken if the PI deems it necessary.

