9.7.1 Data and Safety Monitoring Plan

A committee of three investigators with experience with non-invasive brain stimulation will serve as the Data and Safety Monitoring Committee. The DSMB will meet with the PI every 6 months to review study progress and discuss any adverse events. The BAC group, under the guidance of the faculty statisticians, will provide safety reports every six months to this monitor and the PI. These reports will be blinded as to treatment assignment, unless unblinding for individual events is requested by the monitor. All SAEs will also be reported to the IRB.

10 Study Administration, Data Handling and Record Keeping

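### Section 9.5 orders unblinding after every serious adverse event while 5.3 leaves it to judgement, so the blind can be lost before the 6-month WAB-AQ without a documented need

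*Combined protocol and SAP*

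**What the plan says.** Three places in the combined protocol and SAP deal with breaking the blind.

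- **Section 9.5, Unblinding Procedures.** By default, patients learn which treatment "they received at the completion of the entire study". The exception follows: "If a serious adverse event should occur, the patient will be unblinded/unblinded".
- **Section 5.3, Blinding.** "In the case of an adverse event, the blind may be broken if the PI deems it necessary". The same section keeps the speech-language pathologist, and those who administer and score the language measures, unaware of assignment.
- **Section 9.7.1, Data and Safety Monitoring Plan.** On the six-monthly safety reports: "These reports will be blinded as to treatment assignment, unless unblinding for individual events is requested by the monitor".

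The definitions set how often the 9.5 exception can apply. Section 9.1.2 states "Adverse events are classified as serious or non-serious", and one criterion for serious is that the event "requires or prolongs hospital stay". Section 9.1.1 adds "Inter-current illnesses or injuries should be regarded as adverse events". Section 9.2 records events over the whole study period. The Safety Analysis section (numbered 8.1.4) covers baseline, the two treatment weeks and the following 6 months. The primary endpoint in 3.3.1 and 8.1 is the change in WAB-AQ from the first baseline visit to the 6-month visit.

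**The concern.** Sections 9.5 and 5.3 cover the same events in different terms. One is mandatory and the other discretionary, and neither mentions the other. A coordinator holding the master list when a subject is admitted to hospital cannot tell from the protocol whether the code must be opened or whether the PI decides.

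The mandatory version has a cost for the endpoint. An admission for an unrelated illness in month 4 meets the definition of a serious event, and 9.5 would then open the assignment before the 6-month WAB. If the patient is told, there are three routes to bias:

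- **Expectancy.** The WAB is a behavioural test that depends on effort, and the battery in 7.5 also includes a self-rated communication confidence scale.
- **Missing data.** Section 3.1.3 lets subjects refuse any test without a deviation. Someone who learns that they had sham has less reason to return, so missingness could depend on arm. The primary model in 8.4.1 relies on data being missing at random.
- **Accidental disclosure.** A patient who knows the arm can mention it to a blinded assessor.

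**Working it through.** **1. Do both rules reach the same event?** Section 9.1.2 makes serious events a class of adverse events, so the 5.3 sentence covers them and has no exception for them. For one serious event:

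| | 5.3 | 9.5 |
|---|---|---|
| Force | permissive | mandatory |
| Condition | PI considers it necessary | none |
| Related events only? | not stated | not stated |
| Who learns the assignment | not stated | not clear |
| Cross-reference | none | none |

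They diverge whenever a serious event occurs and the PI sees no need to know the assignment.

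**2. Can this happen before the primary assessment?** Yes. Relatedness is not part of the definition of a serious event (9.1.1, 9.1.2), and events are recorded up to the 6-month visit (9.2 and the Safety Analysis section).

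**3. The plan's own figures.** The plan gives no figure on unblinding and no serious adverse event rate. Its design figure supplies the denominators: 75 evaluable of up to 83 enrolled, allocated 2:1 (50 TMS, 25 sham), with 80% power for 0.7 SD at alpha 0.05 (8.3). Taking alpha as two-sided, a noncentral t calculation with 50 and 25 gives 80.5%, so the figure reproduces. Also 0.7 × 5.7 = 3.99, matching the stated 4 WAB-AQ points. The unblinding point does not depend on this calculation.

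**4. How many subjects?** Let p be the proportion with a serious event before the 6-month visit. This is an assumption, shown over a range. Expected number = p × N.

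| p | N = 75 | N = 83 |
|---|---|---|
| 2% | 1.5 | 1.7 |
| 5% | 3.75 | 4.15 |
| 10% | 7.5 | 8.3 |
| 15% | 11.25 | 12.45 |

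That is about 2 to 12 subjects. At equal rates in the arms, the sham group of 25 would contribute 25 × 0.02 = 0.5 to 25 × 0.15 = 3.75. The lower part of the range is more plausible for the endpoint: the 83 includes 83 − 75 = 8 expected losses, and only events before the 6-month visit in subjects who then take the WAB can affect the score.

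**5. How much could scores move?** Suppose, for illustration, that knowing the arm separated unblinded TMS and sham patients by as much as the design difference of 4 points, with p equal in both arms. The bias in the mean difference would be p × 4: 0.02 × 4 = 0.08 points to 0.15 × 4 = 0.6 points. The documents contain nothing that estimates the true shift, and this sum leaves out any effect through dropout.

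**6. Cost of dropping scores after unblinding.** If the same proportion were removed from each arm, the noncentral t power for 0.7 SD would be 79.7% at 2%, 78.4% at 5%, 76.2% at 10% and 73.7% at 15%. The subset would also be selected on an event after randomisation. Both are reasons to keep such an analysis supplementary.

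**The case against.** The best defence is that the sections can coexist. Section 5.3 contains no word such as *only*, so it can be read as the general permission for adverse events and 9.5 as a specific rule for serious ones. A reader might infer that the two rules cannot both be followed; the text does not go that far. But neither section states this division, and adopting it leaves unrelated hospital stays as an automatic trigger.

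Second, the 9.5 sentence is visibly damaged. The repeated word around the slash suggests that an alternative was lost, so the intended rule is uncertain. It also does not clearly say that the patient is told: it may mean that the allocation is opened to those handling the event. In that case the patient-side routes to bias do not arise. This objection stands, and it is why the consequences are stated conditionally.

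Third, a reader might take 9.7.1 as a further conflicting rule. It governs the blinding of the monitoring board's reports, not what happens to a patient after an event, so it does not add to the conflict.

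Fourth, a reader might infer that 9.5 unblinds the outcome assessors. It does not: 5.3 keeps them and the speech-language pathologist blinded, and 9.5 leaves that in place. Exposure is through what the patient knows or says. Section 8.4.1 also plans shared-parameter and pattern-mixture analyses, which go some way toward arm-dependent dropout.

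Finally, it is tempting to say that unblinding for an unrelated event brings no safety gain. That is a clinical judgement which no section supports, and the point does not need it. It is enough that 9.5 does not ask whether the assignment is needed.

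**Conclusion.** The concern holds in a limited form. Sections 9.5 and 5.3 give different instructions for the same event without reference to each other, and the 9.5 sentence is garbled and unclear about who is told. Because unrelated hospital stays qualify and the window runs to the 6-month visit, 9.5 as written would unblind some subjects before the primary WAB-AQ assessment when the assignment may not be needed.

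The size is modest: about 2 to 12 subjects for assumed rates of 2% to 15% in 75 to 83 subjects, probably toward the lower end. The documents give neither an event rate nor a split into related and unrelated events. The bias routes through expectancy, dropout and disclosure apply if the patient is told. The documents do not show strict incompatibility of the two rules, direct unblinding of assessors, or a measurable bias in the treatment effect. The change is still worth making because the loss of blinding is avoidable and the correction is cheap.

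**What to change.** 1. Reconcile 9.5 with 5.3 so that one rule governs serious and non-serious events, and correct the damaged sentence.
2. Make unblinding conditional on a documented need to know the assignment, rather than automatic for every serious event. Which clinical circumstances meet that condition is for the investigators and the monitoring board to define.
3. State who is told in each case, and separately whether the patient is told. Refer to 5.3 for the continued blinding of the speech-language pathologist and language assessors; no new rule is needed there.
4. Log the date and reason for each unblinding, and who learned the assignment.
5. In 8.4.1, add a supplementary sensitivity analysis addressing WAB scores obtained after unblinding. Leave the primary intent-to-treat analysis unchanged and report the number of such scores by arm.

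The cost is a short protocol amendment, one log and one small additional analysis. Sample size, visits and the primary model do not change.

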9.6 Stopping Rules

The trial may be stopped for safety concerns or poor study performance, including failure to recruit and/or retain subjects. Subjects who report significant discomfort from TMS, seizure, or worsening of language or cognition during TMS will remain in the study with treatment discontinuation. Two sources of information about short-term adverse effects of TMS on language function will be available. First, subjects and family will be asked if they see evidence of deterioration in language or other faculties each day they return for TMS. Second, the SLP will see the subject during each treatment session. S/he will be instructed to inform the PI if s/he observes a clinically significant worsening in language function. If the SLP is concerned, the WAB will be repeated. If this supports a decline from baseline (operationally defined as more than 5 points below baseline), the adverse effect will be reported and the subject will be withdrawn from treatment. In order to support the intention-to-treat analysis, all such subjects will be strongly encouraged to continue follow-up.

9.7 Medical Monitoring

It is the responsibility of the Principal Investigator to oversee the safety of the study. This safety monitoring will include careful assessment and appropriate reporting of adverse events as noted above, as well as the construction and implementation of a site data and safety-monitoring plan. Medical monitoring will include a regular assessment of the number and type of serious adverse events.

9.7.1 Data and Safety Monitoring Plan

A committee of three investigators with experience with non-invasive brain stimulation will serve as the Data and Safety Monitoring Committee. The DSMB will meet with the PI every 6 months to review study progress and discuss any adverse events. The BAC group, under the guidance of the faculty statisticians, will provide safety reports every six months to this monitor and the PI. These reports will be blinded as to treatment assignment, unless unblinding for individual events is requested by the monitor. All SAEs will also be reported to the IRB.

10 Study Administration, Data Handling and Record Keeping

10.1 Confidentiality

Information about study subjects will be kept confidential and managed according to the requirements of the Health Insurance Portability and Accountability Act of 1996 (HIPAA). Those regulations require a signed subject authorization informing the subject of the following:

- What protected health information (PHI) will be collected from subjects in this study
- Who will have access to that information and why
- Who will use or disclose that information
- The rights of a research subject to revoke their authorization for use of their PHI.

PHI (see below) as well as data from the studies to be performed during the study will be kept in an institutionally secured server or in a locked cabinet.

The following protected health information (PHI) will be collected: name, age, contact information (including telephone number), PMH (including information regarding the participant's stroke), SSN, as well as demographic information and results of neuroimaging.

[name] and the research team conducting the study will have access to the subject's PHI as well as data generated during the study. Information contained in publications and presentations will be de-identified. The Institutional Review Board (IRB) as well as the FDA and NIDCD may access information regarding participants should they desire. Although we will strive to protect the privacy of participants, we cannot guarantee absolute privacy.

Subjects will be contacted by the PI to determine if they are interested in participating in the study. Subjects will be referred from multiple sources including colleagues at MossRehab Research Institute, Temple University, and UPHS physicians. Only subjects who have indicated their willingness to consider participating in the study or learn about the study will be contacted by the PI. Most potential subjects will be contacted by the PI who will use the phone script attached to this application.

Subjects will interact with the PI and other members of the research team in the process of obtaining consent, during the testing before and after the treatment as well as during the administration of TMS and CILT.

In the event that a subject revokes authorization to collect or use PHI, the investigator, by regulation, retains the ability to use all information collected prior to the revocation of subject authorization. For subjects that have revoked authorization to collect or use PHI, attempts should be made to obtain permission to collect at least vital status (i.e. that the subject is alive) at the end of their scheduled study period.

10.2 Data Collection and Management

Source documents will be kept in a secure location. Paper-based records will be kept in a locked cabinet and will only be accessible to personnel involved in the study. Most of the information will take the form of computer files; these will be de-identified by using a coding process under which subjects are identified by an assigned subject number. These files will be stored on an institutionally secured and managed device or server. Participants will be voice and video recorded during baseline testing, CIILT treatment, and follow-up testing for the purposes of data analysis. Audio recordings will be transcribed and be saved on password-protected computers. Video recordings will be stored in an encrypted drive to be

used by the study team for data coding and data analysis. All audio and video data will be stored on School of Medicine managed and secured computer devices.

10.3 Records Retention

It is the investigator's responsibility to retain study essential documents for at least 2 years after the last approval of a marketing application in their country and until there are no pending or contemplated marketing applications in their country or at least 2 years have elapsed since the formal discontinuation of clinical development of the investigational product. These documents should be retained for a longer period if required by an agreement with the sponsor. In such an instance, it is the responsibility of the sponsor to inform the investigator/institution as to when these documents no longer need to be retained.

11 Study Monitoring, Auditing, and Inspecting

11.1 Study Monitoring Plan

As noted above, a DSMB consisting of 3 members will be established and will meet with the PI every 6 months

11.2 Auditing and Inspecting

The investigator will permit study-related monitoring, audits, and inspections by the IRB, the sponsor, government regulatory bodies, and University compliance and quality assurance groups of all study related documents (e.g. source documents, regulatory documents, data collection instruments, study data etc.). The investigator will ensure the capability for inspections of applicable study-related facilities (e.g. pharmacy, diagnostic laboratory, etc.).

Participation as an investigator in this study implies acceptance of potential inspection by government regulatory authorities and applicable University compliance and quality assurance offices.

12 Ethical Considerations

This study is to be conducted according to US and international standards of Good Clinical Practice (FDA Title 21 part 312 and International Conference on Harmonization guidelines), applicable government regulations and Institutional research policies and procedures.

This protocol and any amendments will be submitted to the IRB in agreement with local legal prescriptions, for formal approval of the study conduct. The decision of the IRB concerning the conduct of the study will be made in writing to the investigator and a copy of this decision will be provided to the sponsor before commencement of this study.

All patients for this study will be provided a consent form describing this study and providing sufficient information for patients to make an informed decision about their participation in this study. This consent form will be submitted with the protocol for review and approval by the IRB for the study. The formal consent of a patient, using the IRB-approved consent form, will be obtained before that patient is submitted to any study procedure. This consent form will be signed by the patient or legally acceptable surrogate, and the investigator-designated research professional obtaining the consent.

